**Table 4: Variable in cgmanalysis**

Endpoint	Variable in cgmanalysis	Unit
TIR	percent_time_70_180	%
Glucose AUC outside the target range of 70/180 mg/dL	average_auc_70 + average_auc_180	mg/dL/min
MAGE (1 SD)	r_mage	mg/dL
CONGA-1, CONGA-2 and CONGA-4	conga_1, conga_2, conga_4	mg/dL
MODD	modd	mg/dL
Mean daily blood glucose	average_sensor	mg/dL
SD	standard_deviation	mg/dL
2h-PPG	average_auc_per_day*	mg/dL

*\*raw data must be filtered with observations  $\leq$  120 minutes from meals (eDiary)*

# PPD

## 9.3 Partial date conventions

Table 5: Algorithm for Treatment Emergence of Adverse Events

AE START DATE	AE STOP DATE	RULE for TEAE definition	RULE for "Treatment"/"Follow-up" study period definition for TEAE summaries
Known	Known, Partial or Missing	If AE start date < IMP start date, then not TEAE  If AE start date $\geq$ IMP start date, then TEAE	In case of Treatment Discontinuation:  If start date $>$ Date of last IMP intake, then Follow-up study period for TEAE occurrence.  Otherwise, Treatment study period for TEAE occurrence.  In case of NO Treatment Discontinuation:  If start date $\geq$ Date of "Month 12 visit", then Follow-up study period for TEAE occurrence.  Otherwise, Treatment study period for TEAE occurrence.
Partial, but known components show that it cannot be on or after IMP start date	Known, Partial or Missing	Not TEAE	Not Applicable
Partial, could be on or after IMP start date	Known	If AE stop date < IMP start date, then not TEAE  If AE stop date $\geq$ IMP start date, then TEAE	If TEAE, then Treatment study period for TEAE occurrence.

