#### 6.4.2. Criteria for discontinuation of the IMP

The IMP will be discontinued in the case:

- QTcF is either  $> 500$  msec or increases by  $> 60$  msec from screening measurement on two consecutive ECG readings taken 1 hour apart;
- The patient develops any significant cardiovascular disease/abnormality;
- The patient develops renal (calculated eGFR  $< 60$  mL/min) or hepatic (increased ALT/AST  $> 3 \times$  ULN and increased total bilirubin  $> 3$  mg/dL [ $> 51.3 \mu\text{mol/L}$ ]) dysfunction as well as hypoalbuminemia (serum albumin  $< 3$  g/dL);
- Pregnancy occurs (female patient);
- The patient develops any significant systemic infection that must be assessed on a case-by-case basis by the investigator regarding whether they are serious enough to warrant discontinuation.
- The patient develops ketoacidosis or hypoglycemic coma.

Occurrence of any condition that qualify the patient to treatment discontinuation will be specifically monitored through ECG readings and laboratory tests obtained at the visits scheduled at the end of the 3rd (Week 11), 6th (Week 23) and 9th (Week 35) treatment cycles.

In addition, the IMP will be immediately discontinued in the event of any other possibly drug related occurrences that the Investigator believes might compromise patient's safety.

If the IMP administration is prematurely discontinued, the primary reason for discontinuation must be recorded in the eCRF. Patients who discontinue the treatment with the IMP will NOT be withdrawn from the study by default, but will be asked to complete safety and efficacy observations as per the protocol, unless otherwise they withdraw their consent.

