## 3.7 Safety endpoints

The safety endpoints are the following:

- Adverse Events (AEs) and Serious Adverse Events (SAEs) throughout the study;
- Safety Laboratory Tests at Week 11, Week 23, Week 35, Month 12 and Month 18 (or withdrawal);
- Vital signs at Week 11, Week 23, Week 35, Month 12 and Month 18;

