# PPD

## 6. Evaluation of Treatment Compliance and Exposure

### 6.1 Compliance to study treatment regimen

Descriptive analyses of the following parameters will be presented by treatment group for each cycle and during the entire treatment period:

- from IMP dispensation form
  - number of capsules dispensed;
- from IMP accountability form
  - number of returned blisters;
  - number of capsules taken;
  - number of returned unused capsules;
  - IMP intake compliance, ON -treatment period compliance (only by cycle);

Patients are instructed to receive study treatment (either ladarixin or placebo) as follows:

- 400 mg b.i.d (2 capsules at each administration, twice per day);
- for 13 cycles, each lasting 28 days;
- each cycle is composed by 14 consecutive days on-treatment and 14 consecutive days off-treatment.

Calculation of compliance to treatment regimen must consider not only the amount of treatment intake, but also the correct alternation between period “ON” and period “OFF” and their duration. To assess the overall compliance to treatment regimen, the following 3 criteria will be taken into account:

- Compliance to IMP intake;
- Compliance to duration of period “ON” (period of the cycle when the patient is ON treatment);
- Compliance to duration of period “OFF” (period of the cycle when the patient is OFF treatment).

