# PPD

For summaries, the drug-event relationship will be assessed as “None”, “Unlikely”, “Possible” “Probable” or “Highly probable”. Any TEAE reported in the study having a possible, probable or highly probable relationship to IMP will be defined as “Adverse Drug Reaction” (ADR).

The following tables and listings will be presented by treatment group:

- An overview of TEAEs including the number of patients who exhibited at least one TEAE, at least one severe TEAE, at least one serious TEAE, at least one non-serious TEAE, at least one ADR, at least one serious ADR, number of TEAEs, number of non-serious TEAEs, number of TESAEs, number of ADRs, number of serious ADRs, number of deaths, number of patients who discontinued IMP due to a TEAE;
- Summary of TEAEs by primary System Organ Class and Preferred Term and by study period (on treatment/follow-up and overall);
- Summary of TEAEs by primary System Organ Class, Preferred Term and Severity;
- Summary of Serious TEAEs by Primary System Organ Class and Preferred Term and by study period (on treatment/follow-up and overall);
- Summary of ADRs by Primary System Organ Class and Preferred Term and by study period (on treatment/follow-up and overall);
- Summary of ADRs by Primary System Organ Class and Preferred Term and Severity;
- Summary of TEAEs leading to IMP Discontinuation by Primary System Organ Class and Preferred Term and by study period (on treatment/follow-up and overall);
- Summary of TEAEs leading to Death by Primary System Organ Class and Preferred Term and by study period (on treatment/follow-up and overall);
- Listing of all AEs by Patient;
- Listing of SAEs by Patient;
- Listing of ADR by Patient;
- Listing of Deaths.

In addition, time-to-event methods will be used to summarize the time to onset of severe hypoglycemic events from first dose of treatment. Kaplan-Meier estimates and plots will be provided with:

- the 95% confidence interval bounds calculated per the method proposed by Greenwood;
- the respective number of patients at risk and Kaplan-Meier estimates at different time points;
- the median and its 95% confidence interval;
- the log-rank test p-value.

Subjects who have discontinued/completed the study without an event will be censored at the date of discontinuation/completion. In case of patients still ongoing and free from event at the time of DB lock, they will be censored at the DB lock date.

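### SAP Table 5 files an event under Follow-up when its onset falls after the last dose and it leads to discontinuation; the same event in a patient who continues is filed under Treatment

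*SAP*

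**What the plan says.** SAP 9.3, Table 5, assigns each treatment-emergent event with a known start date to one of two study periods. For patients who discontinued, the test is whether the start is later than "Date of last IMP intake, then Follow-up study period for TEAE occurrence". The other branch, headed "In case of NO Treatment Discontinuation", moves events to Follow-up only from the Month 12 visit onward. Events whose start date is partial or missing go to Treatment if they count as treatment-emergent.

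SAP 9.1, Table 3, takes a discontinuer's last dose from the last available diary. Failing that, it uses the date of the visit at which a stopping criterion was reported.

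SAP 6.1 describes the regimen: "each cycle is composed by 14 consecutive days on-treatment and 14 consecutive days off-treatment". Protocol 6.4.2 says how stopping conditions are to be found: "Occurrence of any condition that qualify the patient to treatment discontinuation will be specifically monitored through ECG readings and laboratory tests obtained at the visits" at the end of cycles 3, 6 and 9, that is Weeks 11, 23 and 35. Under protocol 6.2 and 7.3, the kits for the next cycles are released only after that check.

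SAP 8.1 splits five tables by period, each with an overall column: all TEAEs, serious TEAEs, ADRs, TEAEs leading to death, and the "Summary of TEAEs leading to IMP Discontinuation by Primary System Organ Class and Preferred Term and by study period".

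**The concern.** The stopping checks sit in the off-drug half of a cycle. A patient stopped at a check receives no further kits, so the last dose already lies behind the visit. An abnormality dated at that visit starts after the last dose and goes to Follow-up. Had the patient continued, the same abnormality on the same day would be Treatment. The class depends on what was decided after the event and not on exposure when it began.

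The oddest result is in the table of events leading to discontinuation: an event that ended treatment at a planned check appears in the follow-up column. Anyone reading only the on-treatment columns of the five tables would miss it. Enrolment stopped early, so moving one or two events could visibly change a row.

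**Working it through.** **Schedule arithmetic in the SAP.** It reproduces: 14 × 13 = 182 days on drug (6.1.2.1), 14 × 12 = 168 days off drug (6.1.3.1), and 4 × 14 × 13 = 728 capsules (6.1.1.1).

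**Calendar.** With Day 1 as the first dose, cycle c is on drug from day 28(c − 1) + 1 to day 28(c − 1) + 14 and off drug until day 28c. Week w covers days 7(w − 1) + 1 to 7w.

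| Check | On-drug days | Last dose | Visit week | Days after last dose |
|---|---|---|---|---|
| End of cycle 3, Week 11 | 57–70 | 70 | 71–77 | 1–7 |
| End of cycle 6, Week 23 | 141–154 | 154 | 155–161 | 1–7 |
| End of cycle 9, Week 35 | 225–238 | 238 | 239–245 | 1–7 |

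If Week 11 means 11 full weeks after Day 1, the visit is on day 78, 8 days after the last dose and still inside the off interval (days 71–84). The same holds for the other two checks.

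**Applying Table 5 to an abnormality dated day 74:**

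- Patient stopped at the check, diary available: 74 > 70, so Follow-up.
- Patient stopped at the check, diary date unavailable: Table 3 sets the last dose to the visit, day 74. Since 74 > 74 is false, the class is Treatment.
- Patient who continues to Month 12: 74 is before the Month 12 visit, so Treatment.
- Patient stopped at the check, but onset recorded on day 68: 68 is not later than 70, so Treatment.

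The first two lines differ only in whether a diary exists.

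**Off-drug time counted as Treatment in completers.** The last dose is on day 12 × 28 + 14 = 350. With Month 12 on day 52 × 7 = 364 and Follow-up starting that day, days 351–363 count as Treatment. That is 13 days after the final dose. The ±2-week window (days 350 to 378) makes this 0 to 27. Adding the 168 days between cycles gives 168 + 13 = 181 off-drug days in Treatment (range 168 to 195). For discontinuers, no day after the last dose counts.

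**Other definitions in the SAP.** Section 7.2.1.6 treats everything up to Month 12 as the treatment period for severe hypoglycemia. Section 6.1.3.1 counts off-drug days between the last dose and discontinuation within the period assessed for compliance. Section 6.1.2 uses a treatment discontinuation date, and 6.1.2.2 allows that no dose was taken on that day, so it can differ from the last dose.

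**The case against.** A case can be made for two cut-offs. Off-drug days between cycles are part of the regimen for someone who will dose again; a patient who has stopped for good has no further cycles. That stands: the difference in cut-offs is not an error in itself. It does not explain why an event that began before the decision to stop, and caused it, should count as after treatment.

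The effect is also narrower than it may look. A reader might infer that every event found at a stopping check and leading to discontinuation is misfiled. The documents do not support this. Table 5 uses the onset date and not the date of detection, so an event that began on or before the last dose stays in Treatment. So do events with a partial or missing start date, and events dated at the visit when the diary fallback applies. What remains is mainly laboratory or ECG abnormalities dated at the visit, in patients with a diary.

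A reader might also infer that on-treatment harm is understated for ladarixin. That would require more such discontinuations in that arm, which nothing in the documents shows. In the earlier trial in new-onset type 1 diabetes, one of 50 ladarixin patients and one of 26 placebo patients stopped treatment for adverse events, over three cycles (protocol 2.4.2 and 2.4.3). The ladarixin case was a rise in transaminases, which is the kind of event at issue, but one case per arm says nothing about direction.

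Finally, no event is lost. The overall columns, the overview (including its count of patients who discontinued because of a TEAE), the severity tables and the listings are untouched.

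**Conclusion.** The point holds for TEAEs with a known onset after the last dose that lead to discontinuation. For these, Table 5 gives a class that depends on the later decision and on whether a diary date exists. The distortion is confined to the on-treatment/follow-up split in five tables.

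Its size can be given in days but not in events. On schedule, the checks fall 1 to 7 days after the last dose (8 on the alternative reading), and all of those days count as Follow-up for a patient stopped there. The protocol's own clearance time, about 98 hours or some 4 days (2.5.1), covers roughly the first half of that interval. The number of events may be small.

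Assumptions: dosing on the ideal calendar, visits within the named weeks (no window is given for Weeks 11, 23 and 35), and abnormalities dated at the visit at which they were found.

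This is worth correcting because the affected events are those that ended treatment. It does not change any overall safety count.

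**What to change.** In the discontinuation branch of Table 5, classify an event as Follow-up only if its start date is later than the later of (a) the date of last IMP intake and (b) the recorded date of treatment discontinuation. A TEAE that leads to discontinuation, with onset up to that date, then counts under Treatment whether or not the diary is available. Leave the completers' rule unchanged.

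Confirm that the recorded discontinuation date is the date of the decision and not a copy of the last-dose date; otherwise the change has no effect.

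The cost is one cell and a rerun of five tables, with no new data. Some off-drug days before the decision will count as Treatment, as off-drug days already do for patients who continue. At a scheduled check this is a few days. It could be longer if a patient stops taking capsules and the decision is recorded only at a later contact, so list the gap for each discontinuer.

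Extending Treatment to last dose plus 14 days for everyone is possible but is a matter of choice, and it would reclassify completers too. With Month 12 on day 364, day 364 itself would move into Treatment; with the visit on day 378, days 365–377 would move out.

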## 8. Evaluation of Safety

### 8.1 Adverse events

Any AE which starts at or after the first administration of study treatment will be considered a Treatment Emergent Adverse Event (TEAE). Pre-treatment AEs and TEAEs will be presented separately. Pre-treatment AEs will be presented in the listings only. In case of missing or incomplete dates not allowing a direct allocation to any of the two categories of AEs, a worst-case allocation will be done according to the available parts of the onset and the end dates (see Table 5). The AE will be allocated to the first category allowed by the available data, according to the following order:

- TEAE;
- Pre-treatment AE.

In case of TEAE, the event can be classified as:

- On Treatment Period, or
- On Follow-up period

according to the available parts of the onset and the end dates (see Table 5).

All AEs will be assigned to a Preferred Term (PT) and will be classified by primary System Organ Class (SOC) according to the MedDRA thesaurus. In addition, each AE will be graded according to severity definitions as "Mild", "Moderate" or "Severe".

TEAEs summaries will be presented, displaying frequencies and percentages of patients reporting AEs. In the summaries, primary SOC will be presented alphabetically and the PT will be sorted within SOC in descending overall frequencies .

Along with AEs, number of events will be reported. On each of these summaries, patients will be counted only once per SOC and, within each SOC, patients will be counted only once per PT.

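### SAP Table 5 files a TEAE with a partial start date under Treatment even when its known month and year lie wholly in follow-up

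*SAP*

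**What the plan says.** SAP 8.1 divides TEAEs into an on-treatment and a follow-up period and says this is done "according to the available parts of the onset and the end dates (see Table 5").

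Table 5 in SAP 9.3 gives the rules:

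- **Known start date, treatment discontinued:** "If start date $>$ Date of last IMP intake, then Follow-up study period for TEAE occurrence"; otherwise *Treatment*.
- **Known start date, treatment not discontinued:** *Follow-up* from the date of the Month 12 visit onward; otherwise *Treatment*.
- **Partial start date, excluded as pre-dose** ("Partial, but known components show that it cannot be on or after IMP start date"): not a TEAE, so no period applies.
- **Partial start date, not excluded** ("Partial, could be on or after IMP start date"): TEAE status is settled from the stop date, and then "If TEAE, then Treatment study period for TEAE occurrence".
- **Missing start date:** the same period rule.

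The split feeds five tables in SAP 8.1: TEAEs, serious TEAEs, ADRs, TEAEs leading to IMP discontinuation and TEAEs leading to death. The first is specified as "Summary of TEAEs by primary System Organ Class and Preferred Term and by study period (on treatment/follow-up and overall").

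**The concern.** Table 5 uses the known parts of a partial start date at one end only. They can show that an event began before the first dose. They cannot show that it began after the treatment period ended, because the row for dates possibly on or after IMP start has no upper limit and a single outcome. Two events with onset in the same follow-up month can therefore land in different columns, depending only on whether the day was recorded.

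At stake is the split in the five by-period tables: *Treatment* is over-counted and *Follow-up* under-counted by the same events. Follow-up events will exist. Protocol 8.3 collects AEs to the last planned visit, and Protocol 6.4.2 and 7.5.1 keep patients who stop IMP under observation, apart from withdrawals of consent and pregnancies.

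**Working it through.** The SAP states no figure for this rule, so there is none to reproduce. The check applies Table 5's two rules to the same event.

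**Inputs.** Month 12 = Week 52 and Month 18 = Week 78 (SAP 3.2); 13 cycles of 28 days, each starting with 14 days on drug (SAP 6.1); cut-offs from Table 5. First-dose dates are assumed, and visits are taken at their nominal weeks.

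**One case.** First dose 10 Jan 2021, all cycles taken.

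- Last dose: 12 × 28 + 13 = 349 days later, 25 Dec 2021.
- Month 12 visit: 52 × 7 = 364 days later, 9 Jan 2022.
- Month 18 visit: 78 × 7 = 546 days later, 10 Jul 2022.
- AE onset recorded as April 2022, day unknown: possible dates are 1 to 30 April 2022.
- Known-date rule: *Follow-up* for 1 April and for 30 April, hence for every possible day.
- Partial-date rule: *Treatment*.

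**How often month and year settle the matter.** Take *Follow-up* as settled when the first day of the recorded month already meets the cut-off. In this case follow-up runs from 9 Jan to 10 Jul 2022, 546 − 364 + 1 = 183 days. Only 9–31 January (23 days) shares a month with the treatment period, so (183 − 23)/183 = 160/183 = 87% of follow-up days are settled. Repeating this for every first-dose date in 2021 gives:

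| Patient | Follow-up days | Settled by month and year: mean (range) | Assigned *Follow-up* by Table 5 as written |
|---|---|---|---|
| Completes treatment | 183 | 92% (84–100%) | 0% |
| Stops after cycle 3 | 477 | 97% (94–100%) | 0% |
| Stops after cycle 6 | 393 | 96% (92–100%) | 0% |
| Stops after cycle 9 | 309 | 95% (90–100%) | 0% |

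**Illustrative size.** For completers, follow-up is (78 − 52)/78 = 33% of post-dose time. With evenly spread onsets, 0.333 × 0.92 = 31% of TEAEs dated to month and year only would be misfiled. The documents give no rate of partial dates. At an assumed 2% the share of all TEAEs is 0.02 × 0.31 = 0.6%; at 5% it is 0.05 × 0.31 = 1.5%. A patient who stops early has a longer follow-up and a larger share: stopping after cycle 3 (70 days, 10 weeks) leaves 78 − 10 = 68 of 78 weeks in follow-up.

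**What the stop date adds.** An end date bounds onset from above only. It can show that an event began during treatment, never that it began in follow-up. The start date's known parts are the only evidence for *Follow-up*, and Table 5 does not use them for this.

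**The case against.** The best defence is that the default is cautious: where dates are incomplete, the event is charged to treatment, in the spirit of the worst-case allocation in SAP 8.1. That allocation, however, is written for TEAE versus pre-treatment AE, and only "In case of missing or incomplete dates not allowing a direct allocation to any of the two categories of AEs". When month and year lie wholly beyond the cut-off, direct allocation is possible. The caution also works in one column only, because each event added to *Treatment* is lost from *Follow-up*.

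The points about consequence largely stand. TEAE status and the overall column do not change. AEs, SAEs, ADRs and deaths are listed by patient (SAP 8.1), and partial dates are shown with dashes (SAP 10.1), so a misfiled event can be found. Onset dates are collected (Protocol 8.3) and missing data are queried (Protocol 11.3). All analyses are now descriptive (SAP 4.8), and no decision rule uses the split.

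Two stronger readings are tempting and do not hold:

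- **Every partial or missing start date is mishandled.** A fully missing date has no known parts, and a date limited to the cut-off month, or usually to a year, leaves both periods possible. *Treatment* is a defensible default for all of these.
- **Off-drug events are credited to an on-drug column that serves to show whether events stop when drug stops.** *Treatment* is not an on-drug column: half of each cycle is off drug by design, and a completer's events between the last capsule and the Month 12 visit count there too. No section states that use for the follow-up column.

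In the text as read, the period cells for partial or missing stop dates are blank, apparently one merged cell broken across pages. The row with a known stop date suffices for the point.

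**Conclusion.** Wrong as written, minor impact. For partial start dates whose known parts lie wholly after the cut-off, Table 5 gives a label that its own known-date rule would reverse on every possible day, and it departs from the principle stated in SAP 8.1. That conclusion rests on the text alone.

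The size is uncertain. The figure of roughly 0.6–1.5% of TEAEs assumes a 2–5% partial-date rate, month and year always known, even onset, nominal visit dates and full completion; none of these comes from the trial's data. Early stopping would raise it, and more complete dates would lower it. A reader might also infer a bias between arms. The rule is the same in both, and the documents give no basis for a direction.

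**What to change.** Add one row to Table 5 for partial start dates. Take the earliest date consistent with the known components (first of the month, or 1 January if only the year is known). If that date is after last IMP intake (treatment discontinued), or on or after the Month 12 visit (not discontinued), assign *Follow-up*. Keep *Treatment* for fully missing start dates and for partial dates that leave both periods possible. Show explicitly that the period rule also covers the rows with a partial or missing stop date.

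The cost is one table row and about one line of code, with no new data. If the tables have already been produced, rerun the five by-period summaries and record the change in the clinical study report, as SAP section 1 requires for deviations.
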